3.3 ASSESSMENT OF DEVICE INTEGRITY AND PERFORMANCE

Criteria for assessment of device integrity and performance include:

- Significant Clotting within the Device as assessed by visual inspection
- Evidence of leakage (i.e., cracking/breakage of a port, connector, hemofilter cartridge or tubing).
- Any unforeseen malfunction that results in the need for discontinuation.

4. STUDY DESIGN

This is an open-label, multi-center Pilot Study.

5. SELECTION OF PATIENT POPULATION

5.1 STUDY POPULATION

Up to 30 pediatric patients will be enrolled in this study, in up to 10 Clinical Centers in the United States.

Pediatric patients with a body weight (BW) greater than or equal to 15 kg receiving care in the Intensive Care Units of each participating hospital will be screened daily and identified for participation in the trial. See **Appendix E**, CRRT Management.

5.2 INCLUSION CRITERIA

1. A patient, or legal representative, has signed a written informed consent form.
2. Must be receiving medical care in an intensive care unit (e.g., ICU, PICU, CICU, Trauma).
3. Age less than 22 years.
4. Females of child bearing potential who are not pregnant (confirmed by a negative serum pregnancy test) and not lactating if recently post-partum.
5. Intent to deliver full supportive care through aggressive management utilizing all available therapies for a minimum of 96 hours.

6. Clinical diagnosis of AKI due to etiologies requiring CRRT (see Appendix B). AKI is defined as acute kidney injury with any one of the following:
 - Increase in SCr by ≥ 0.3 mg/dL (≥ 26.5 μ mol/L) within 48 hours or;
 - Increase in SCr to ≥ 1.5 times baseline, which is known or presumed to have occurred within the prior 7 days or;
 - Urine volume <0.5 ml/kg/h for 6 hours
7. At least one non-renal organ failure (defined as receiving mechanical ventilation or at least one vasoactive medication to treat hypotension) OR presence (proven or suspected) of sepsis (**Appendix C**).

5.3 EXCLUSION CRITERIA

1. Threshold blood pressure of 80/40 mmHg-- patients with both a systolic blood pressure of less than 80 mmHg and a diastolic blood pressure of less than 40 mmHg.
2. Irreversible brain damage based on available historical and clinical information.
3. Patients with a solid organ transplant or those with a bone marrow or stem cell transplant in the previous 100 days or who have not engrafted.
4. Acute or chronic use of circulatory support device, other than ECMO, such as LVADs, RVADs, BIVADs.
5. Presence of preexisting advanced chronic renal failure (i.e., ESRD) requiring chronic renal replacement therapy prior to this episode of acute kidney injury or with pre-existing chronic kidney disease (CKD) defined as a eGFR <30 ml/min/1.73m 2 . Patients who have never seen a pediatric nephrologist will be assumed not to have pre-existing CKD.
6. AKI occurring in the setting of burns, obstructive uropathy, vasculitis, scleroderma renal crisis, atheroembolism, functional or surgical nephrectomy, cyclosporine or tacrolimus nephrotoxicity.
7. Received >12 hour of CRRT (not including SCUF on ECMO) during this hospital admission or prior to transfer from an outside hospital.
8. Received >1 hemodialysis treatment during this hospital admission or prior to transfer from an outside hospital.
9. Metastatic malignancy which is actively being treated or may be treated by chemotherapy or radiation during the subsequent three month period after study therapy.
10. Chronic immunosuppression with the exception of corticosteroids up to a dose of 10 mg per day.
11. HIV or AIDS.
12. Severe chronic liver failure as determined by standard diagnostic requirements.

13. Current Do not Attempt Resuscitation (DNAR), Allow Natural Death (AND), or withdrawal of care status, or anticipated change in status within the next 7 days.
14. Patient not expected to survive 28 days because of an irreversible medical condition. (This is not restrictive to AKI, and may include situations such as the presence of irreversible brain damage, untreatable malignancy, inoperable life threatening condition, or any condition to which therapy is regarded as futile by the PI.)
15. Any medical condition that the Investigator thinks may interfere with the study objectives.
16. Physician refusal.
17. Dry weight <15 kg.
18. Platelet count <15,000/mm³.
19. Concurrent enrollment in another interventional clinical trial. Patients enrolled in clinical trials where only measurements and or samples are taken (NO TEST DEVICE OR TEST DRUG USED) are allowed to participate.
20. Use of any other interventional drug or device within the previous 30 days.

6. STUDY ACTIVITIES

6.1 SCREENING PERIOD

The screening period is the time period when a patient is identified, informed consent is obtained, and the patient is evaluated for inclusion in the clinical trial. Because of the critically ill nature of the study population, it is expected that the majority of patients will not be able to provide informed consent. Where subjects are unable to consent themselves, surrogate informed consent will be sought from the subject's healthcare proxy or other equivalent legal representative. Only adverse events directly related to the screening procedures will be reported during this time.

Medical history and test results must be examined to ensure the patient meets all eligibility criteria. Tests that are specific to this protocol (i.e. not standard of care) require the patient or legal representative to have provided written consent for participation.

Any patients that do not meet study criteria, whether consent was obtained or not, will not be enrolled into the study. These patients will not be counted in the overall study enrollment numbers, but will be listed on the screening log.

Prior to enrollment please contact the study sponsor to validate that the patient has met all inclusion and exclusion criteria.

Chief Medical Officer: [name] [contact]
OR

[name] [contact], [contact]
Cincinnati Children's Hospital Medical Center (CCHMC)

6.2 CRRT PARAMETERS

6.2.1 CITRATE ANTICOAGULATION

Each participating clinical site will use their regional citrate anticoagulation protocol. The clinical site is responsible to achieve, and maintain a serum post filter ionized calcium level of <0.40 mmol/L throughout the entire observation period (day and night). The serum post filter ionized calcium level will be collected from the CRRT Circuit post SCD [REDACTED]

To alleviate the metabolic derangements associated with regional citrate based anticoagulation:

- a) *Alkalosis:* Patients with an arterial pH <7.40 at enrollment will initiate CRRT with solutions containing either 25 or 35 meq/L

of base as directed by local standard of care. During the study, if the patient's arterial pH increases to >7.45 OR the patient's serum bicarbonate increases to >35 meq/L, the CRRT solution will be changed to a base concentration of 25 meq/L, OR 0.9% NaCl will be added dialysis fluid to correct the alkalosis per local standard of care.

b) *Citrate lock:* If the patient develops citrate lock, as defined by a serum ionCa <0.95 mmol/L and a total serum Ca >12.5 meq/L, the citrate infusion will be discontinued OR the CRRT clearance will be increased by 50% per local standard of care, AND CRRT circuit Ca and patient Ca will be checked at least every one hour. For centers that stop citrate, once the patient ionCa is >1.0 mmol/L, the citrate will be restarted at 50% of the previous rate, and hourly ionCa pairs will be rechecked x 3 to ensure a stable patient ionCa >1 mmol/L and stable circuit ionCa <0.40 mmol/L.

Of importance the clinical plan is to monitor the perfusion circuit iCa levels at least q1h at the initiation of regional citrate anticoagulation (RCA) until a steady state iCa range is between 0.25 to 0.40 mmol/L. Once established, iCa levels both in the circuit and in the patient will be monitored q6h. If the iCa is outside the targeted range or alterations in citrate or calcium infusion rates are made, iCa levels are measured at least q1h until targeted ranges are once again achieved. Of importance, for efficacy of SCD treatment, iCa levels must be maintained in the recommended range at least 90% of the time, based on a sensitivity analysis showing that the mortality endpoint difference was lower with target iCa 80-85% of total treatment in clinical trial SCD-003.

The protocol example identified in **Appendix K** may be utilized.

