7.2. TREATMENT DISCONTINUATION CRITERIA

Patients may be withdrawn from therapy prior to hour 168 for a variety of reasons. When therapy is discontinued prior to hour 168, the follow-up period will immediately begin and data will continue to be collected per protocol.

The Principal Investigator will assign a primary reason for therapy termination utilizing the categories listed in 7.3 and 7.4 below, and if appropriate, one or more subcategories.

7.3. CLINICAL CRITERIA:

1. Improvement in Clinical Status

If a patient's condition improves (e.g. renal condition has improved to the extent that CRRT can be discontinued or hemodynamic status has improved so that the dialysis modality can be changed from CRRT to IHD) treatment may be discontinued before the 168 hour treatment period. The decision to discontinue treatment based upon improvement in clinical status will be made by the Principal Investigator.

2. CRRT related medical events

Such as persistent leukopenia, neutropenia or thrombocytopenia based upon PI's clinical assessment.

3. SCD related medical events

Such as persistent leukopenia, neutropenia or thrombocytopenia based upon PI's clinical assessment of relationship to SCD.

4. CRRT Failure/Malfunction

Failure of the CRRT device and/or circuit, including inability to maintain vascular access that requires treatment to be discontinued prior to hour 168 of therapy.

5. SCD Failure/Malfunction

Any failure of the SCD █ that requires treatment to be discontinued prior to hour 168 of therapy e.g. clotting or evidence of leakage in the SCD █ or inability to maintain a patent circuit.

6. Death**7. Withdrawal of life support****8. Concomitant Medical Conditions**

Need for medical, surgical or diagnostic procedures that necessitate discontinuation of SCD treatment for longer than the allowable 12 hours per 24 hour period.

9. Regional Citrate Anticoagulation Intolerance

All patients must be able to tolerate and achieve satisfactory regional citrate anticoagulation. Tolerance of regional citrate anticoagulation is defined as achieving:

- Two (2) consecutive circuit ionized calcium levels of < 0.40 mmol/L (or < 1.6 mg/dL),
- At least 30 minutes apart, and
- Within the first 12 hours of CRRT initiation.

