15. APPENDICES

APPENDIX A – PEDIATRIC RISK OF MORTALITY (PRISM II) SCORE ^[27]

ORGAN SYSTEM	MEASURE
Respiration	PaO ₂ to FiO ₂ Ratio, P _a CO ₂ , Resp. Rate
Coagulation	Protime, PTT
Liver	Serum Total Bilirubin
Cardiovascular	Systolic BP, Diastolic BP, Heart rate
Central nervous system	Glasgow Coma Score, Pupillary Reflexes
Metabolic	Serum potassium, calcium, glucose, bicarbonate glucose

ORGAN SYSTEM	MEASURE	FINDING	POINTS
Respiration	PaO ₂ to FiO ₂ Ratio (please see Pulmonary System Conversion Table for Non-ventilated Pts)	200 – 300 mmHg	2
		<200 mmHg	3
	P _a CO ₂	51-65 mmHg	1
		>65	5
	Respiratory Rate (breath/min)	51-70	1
		>70 or Apnea	5
Coagulation	Protime or Partial Thromboplastin Time	1.5 x control	2
Liver	Serum Total Bilirubin	>3.5 mg/dL	6
Cardiovascular	Systolic Blood Pressure (mmHg)	150-200 or 65-75	2
		>200 or 50-64	6
	Diastolic Blood Pressure (mmHg)	>110	6
	Heart Rate (beat/min)	>150 or <80	4
Central Nervous System	Glasgow Coma Score	<8	6
	Pupillary Reactions	Unequal or dilated	4
		Fixed and dilated	10
Metabolic	Potassium (mEq/L)	3.0 – 3.5 or 6.5 – 7.5	1
		<3.0 or >7.5	5
	Calcium (mg/dL)	7.0 – 8.0	2
		12.0 – 15.0 or <7.0	6
	Glucose (mg/dL)	40-60 or 250 – 400	8
		<40 or >400	8
	Bicarbonate (mEq/L)	<16 or >32	3

Conventions used for the above table include:

- PaO₂ is in mmHg and FiO₂ in percent from 0.21 to 1.00.

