 - i. 50 ml/hour as post-filter replacement fluid via the replacement fluid pump using (PrismaSolTM). This is necessary to prevent clotting of the deaeration chamber (50 ml/hour is the lowest allowable rate)
 - ii. The remaining fluid rate (total replacement fluid rate – 50 ml/hour) pre-filter replacement fluid via the pre-blood pump (PBP) using PrismaSolTM.
 - c. The composition of PrismaSateTM and PrismaSolTM should be equivalent. Any additives (e.g. potassium chloride) should be added in equivalent concentrations to both dialysis and replacement solutions.

3. Regional citrate anticoagulation: All CRRT circuits will receive regional citrate anticoagulation. The initial prescription and calcium level monitoring will be based on the size of patients and the presence, or lack thereof, of significant hepatic dysfunction. **REMEMBER TO ACCOUNT FOR THESE FLUIDS IN THE PATIENT REMOVAL RATE AS THESE ARE EXTERNAL TO THE CRRT MACHINE.**

a. Patients > 1 year of age and with normal hepatic function:

- i. Order ACD-A™ and CaCl₂ (8 grams/1 liter NS) to bedside
- ii. Initial ACD-A™ rate = 1.5 x CRRT blood pump rate x min/hour (e.g., if blood pump rate is 100 ml/minute; the ACD-A™ rate is 150 ml/hour). This is to be infused at a stopcock or y-connector on access line.
- iii. Initial CaCl₂ rate = 0.6 x blood pump rate x min/hour (e.g., if blood pump rate is 100 ml/minute; the CaCl₂ rate is 60 ml/hour).
- iv. Calcium monitoring schedule
 1. Check patient total and ionized calcium prior to CRRT initiation.
 2. Check patient and system ionized calcium 5 minutes after CRRT settings at prescribed rates.
 3. Check patient and system ionized calcium 2 hours after CRRT settings at prescribed rates.
 4. Check patient and system ionized calcium every 8 hours thereafter
 5. Check patient total calcium daily
 6. Check patient and system ionized calcium one hour after any change in ACD-A™ or CaCl₂ rate

b. Desired Calcium Concentration ranges

- i. Circuit ionized calcium = 0.25 to 0.40 mmol/L
- ii. Patient ionized calcium = 1.1 to 1.3 mmol/L (a higher level may be requested by ICU/CICU service if clinically indicated)
- iii. Patient systemic calcium = 8 to 12 mg/dL

c. Citrate anticoagulation management

- i. Bedside RN to call for patient ionCa < 1 mmol/L or > 1.5 mmol/L, or circuit ionCa < 0.25 mmol/L or > 0.40 mmol/L
- ii. Circuit ionCa managed with ACD-A™ rate
 1. For circuit ionCa < 0.25 mmol/L, decrease ACD-A™ 10%
 2. For circuit ionCa > 0.40 mmol/L, increase ACD-A™ 10%

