- iii. Patient ionCa managed by CaCl₂ rate
 1. For patient ionCa < 0.9, increase CaCl₂ 20%
 2. For patient ionCa 0.9- 1, increase CaCl₂ 10%

3. For patient ion Ca 1.3-1.5, decrease CaCl₂ 10%
4. For patient ion Ca > 1.5, decrease CaCl₂ 20%

- 4. Access Size: (per clinical investigator decision)**
- 5. Blood pump flow rate: The minimum blood pump flow rate should be 50 ml/minute to prevent circuit clotting unless not clinically tolerated:**
 - a. Neonate/Infants – 8 to 12 ml/kg/minute
 - b. Toddlers – 6 to 8 ml/kg/minute
 - c. Older children and adolescents – 3-6 ml/kg/minute
- 6. 3-hour Fluid Balance Safety Limit: Limits set to prevent < 5% of blood volume error over 3 hours for smaller patients and < 10% over three hours for larger patients**
 - a. Patients < 30 kg – 150 ml
 - b. Patients 30-50 kg – 200 ml
 - c. Patients > 50 kg – 300 ml
- 7. Scheduled circuit changes: Circuits should be changed no later than every 72 hours, as this is the maximum interval at which the machine has been tested by the manufacturer for accuracy. Any diversion from this recommendation must have rationale documented in the medical record. The following situations serve as examples:**
 - a. The patient has a do not resuscitate or do not escalate care order that was placed on the chart while the patient is receiving CRRT.
 - b. The patient is so clinically unstable that the patient will likely not tolerate stopping and restarting CRRT.
- 8. Blood priming at CRRT initiation and blood return at CRRT termination**
 - a. Blood priming of the CRRT circuit should be done if the extracorporeal volume of the circuit is > 10% of the patient's blood volume.
 - b. Blood should not be returned to the patient at CRRT termination when circuits are blood primed unless specifically requested by the physician in a separate order.

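### The total-calcium limit in the citrate-lock rule (Section 6.2.1(b)) equals 25 mg/dL as printed, so the rule would rarely if ever trigger; the unit was probably meant to be mg/dL

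*Combined protocol and SAP*

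**What the plan says.** Section 6.2.1 lets each site run its own regional citrate protocol and makes the site responsible for holding circuit ionized calcium below 0.40 mmol/L day and night. Item (b) then fixes a definition of citrate lock for the whole trial: "as defined by a serum ionCa <0.95 mmol/L and a total serum Ca >12.5 meq/L". When it is met, "the citrate infusion will be discontinued OR the CRRT clearance will be increased by 50% per local standard of care", with circuit and patient calcium checked at least hourly. No other definition of citrate lock appears in the document.

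The other places that bear on the unit are these:

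- Section 7.3 item 9 supplies a conversion, in its requirement for "circuit ionized calcium levels of < 0.40 mmol/L (or < 1.6 mg/dL".
- Appendix A scores calcium in mg/dL, and its most extreme row reads "12.0 – 15.0 or <7.0".
- Appendix K item 3b gives "Patient systemic calcium = 8 to 12 mg/dL" as a desired range, with patient ionized calcium of 1.1 to 1.3 mmol/L. Appendix K is optional: the sentence in Section 6.2.1 that begins "The protocol example identified in" only permits its use.

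**The concern.** The two conditions are joined by *and*. If the total-calcium limit cannot realistically be reached, the required response is never called for, however low the ionized calcium falls. A limit of 12.5 looks natural in mg/dL but very high in meq/L. Item (a), directly above, uses meq/L properly for base and bicarbonate, so a unit carried down from there is a plausible cause.

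Safety is the primary objective, and the patients are critically ill children on continuous citrate for up to seven days. The protocol also presses sites to keep citrate running. Ionized calcium is to be in range at least 90% of the time, and Section 8 lists failure to hold circuit calcium below 0.40 mmol/L among the grounds for closing a site. The citrate-lock rule is the counterweight to that pressure, so its threshold needs to be reachable. Calcium disturbance has occurred with this device: Table 2 lists eight hypercalcemia events (6 mild, 2 moderate) in nine patients, although none is described as citrate lock.

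**Working it through.** The plan does not derive the 12.5 limit, so there is no calculation of its own to reproduce. The check is a unit conversion.

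**Inputs**

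- Trigger: ionized calcium below 0.95 mmol/L and total calcium above 12.5 meq/L (Section 6.2.1(b)).
- Conversion: 0.40 mmol/L = 1.6 mg/dL (Section 7.3 item 9).
- Comparators: total calcium 8 to 12 mg/dL and ionized calcium 1.1 to 1.3 mmol/L (Appendix K item 3b); highest PRISM II band 12.0 to 15.0 mg/dL (Appendix A).
- Calcium has valence 2, so 1 mmol = 2 meq. This is a chemical constant that the protocol does not state.

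**Conversion factor**

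1.6 / 0.40 = 4 mg/dL per mmol/L. The atomic weight gives 4.0078, so the protocol's factor is sound.

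**Limit as printed**

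12.5 meq/L / 2 = 6.25 mmol/L; 6.25 × 4 = 25 mg/dL (25.05 with the exact factor).

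- Against the top of the desired range: 25 / 12 = 2.08.
- Against the top of the highest PRISM II band: 25 / 15 = 1.67.

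**Limit if the unit is mg/dL**

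12.5 / 4 = 3.125 mmol/L, or 6.25 meq/L. This lies just above 12 mg/dL and inside the 12.0 to 15.0 band.

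**Limit if the unit is mmol/L**

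12.5 × 4 = 50 mg/dL, which is not a credible alternative.

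**Ratio of total to ionized calcium at the trigger (both in mmol/L)**

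| Case | Calculation | Ratio |
|---|---|---|
| As printed | 6.25 / 0.95 | 6.6 |
| If mg/dL | 3.125 / 0.95 | 3.3 |
| Appendix K ranges, lowest | (8/4) / 1.3 = 2 / 1.3 | 1.5 |
| Appendix K ranges, highest | (12/4) / 1.1 = 3 / 1.1 | 2.7 |

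The protocol sets no criterion on this ratio, so the table is descriptive. It shows that the mg/dL reading puts the trigger just outside what the desired ranges allow, while the printed unit puts it at more than twice their highest ratio.

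**The case against.** The case on the other side accepts the arithmetic and the likely slip, and disputes how much it matters.

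- *Staff may read it as intended.* If laboratories report in mg/dL, a clinician may simply compare the result with 12.5. That is possible, but the protocol does not state laboratory units, and a safety rule should not depend on being misread in the right direction.
- *Local practice governs.* Sites follow their own citrate protocols, may act earlier, and may stop study treatment for any reason the investigator thinks fit (Section 7.3 item 10). This stands as mitigation. Item (b) leaves the choice of response to the site but fixes the definition itself.
- *Low ionized calcium would be noticed anyway.* Section 6.2.1 has circuit and patient levels checked every 6 hours, and at least hourly when out of range. Appendix K item 3c has the nurse call when patient ionized calcium falls below 1 mmol/L, whatever the total. These safeguards are real and come before the 0.95 limit. However, the checks are monitoring only, Appendix K is optional, and its listed response is to raise the calcium chloride rate (by 10% at 0.9 to 1, by 20% below 0.9), not to reduce citrate.
- *The correct value is inferred.* No passage states 12.5 mg/dL as a citrate-lock limit; the comparators are a target range and a severity score. This stands, and is why the correction needs clinical confirmation.
- *No endpoint is shown to be biased.* Also true. This is a patient-safety point, not an inferential one.

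**Conclusion.** The concern holds: the threshold is wrong as written. It equals 25 mg/dL, about twice any total-calcium level the protocol treats as a target and 1.7 times the highest level its severity score lists. Because low ionized calcium is also required, the mandatory response would in effect not be triggered. The safeguards elsewhere reduce the likely harm but leave the trial-wide definition uncorrected.

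The conversion is certain. Two further statements are inference. That the limit would rarely if ever be met rests on its size, since the protocol gives no frequencies. That mg/dL was intended rests on 12.5 falling just above the desired range, and on serum calcium being in mg/dL in both Appendix A and Appendix K. A wrong number in a required safety rule for children, correctable at almost no cost, must be fixed.

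**What to change.** In Section 6.2.1(b), change the total-calcium limit to >12.5 mg/dL (about 3.1 mmol/L), after the sponsor's clinical lead confirms that value, and notify all sites. The cost is one unit in a protocol amendment and a site notice, with no effect on sample size, data collection or timelines.

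Two minor corrections could go in the same amendment; neither bears on the conclusion above.

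- Appendix L, HF 700 table: the 30 to 50 kg row should end at 47 kg. The circuit is 329 ml, and 329 / (0.10 × 70) = 47.0 kg; the row's own 3290 ml agrees.
- Appendix K item 6 (optional): the 150 ml limit under 30 kg exceeds the stated 5% of blood volume. It is 150 / (70 × 15) = 14.3% at 15 kg and 150 / (70 × 30) = 7.1% at 30 kg. Lower the limit for the smallest patients or restate the percentage.

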6.2.2 BLOOD CIRCUIT VOLUME

The additional blood volume for the SCD is 120 ml. This additional circuit blood volume for the standard SCD in >20 kg patients can be handled with blood priming with matched blood similar to the standard practice in neonates. Blood prime will occur if the total extracorporeal circuit volume (ECV) is greater than 10% of the patient's blood volume, based on an estimate of blood volume = 70 ml/kg x patient body weight (kg) [24]. The situation is most commonly encountered in neonatal CRRT, where circuit ECV can represent nearly 50% of patient blood volume, yet the same principles apply for this clinical study. [25]

Hypotension associated with blood priming can occur from transient dilution of vasoactive medications (e.g., norepinephrine), or from exposure to the hyperkalemic, hypocalcemic acidotic nature of blood banked blood, which can cause a bradykinin release syndrome (BRS) when the blood is exposed to the CRRT membrane. The BRS is usually associated with AN-69 membranes that will not be used in this study. Each center has its own blood priming protocol to mitigate the potential for this reaction. However, minimum standards for blood priming in this trial are detailed in Appendix L to ensure patient safety. [26]

Patients with AKI requiring CRRT are often hypotensive prior to initiation of CRRT. Initiation of CRRT itself can improve hemodynamics by correcting acidosis and hypocalcemia. Most patients with hemodynamic instability receive vasoactive medications. Since the age range and associated normal blood pressure parameters is wide for this pediatric study, it is difficult to mandate an age specific lower blood pressure threshold to preclude CRRT initiation, especially if CRRT can address the instability as noted above. However, a threshold BP of 80/40 mmHg-- patients with both a systolic blood pressure of less than 80 mmHg and a diastolic blood pressure of less than 40 mmHg will not be entered into the study.

If a patient develops hypotension or experiences worsening hypotension during CRRT/SCD initiation (defined as a > 10 mmHg decrease in mean arterial pressure (MAP) during the first 15 minutes of CRRT initiation or integration of the SCD into the circuit), the patient will receive a 10 ml/kg crystalloid bolus over 10 minutes. If this bolus does not lead to improvement of MAP within 5 minutes, vasoactive medications will either have their dose increased (if already prescribed) or will be initiated. Each center will select the vasoactive medication that is best suited for the clinical indication.

